Data was routinely prospectively collected on paper based patient forms in the clinical setting at EH. A *patient database* with consecutive patients treated between October 17, 2016 and July 31, 2017 was created. It is expected that the database will contain a total of 1,800 patients to produce approximately 160 evaluable subjects. Paper based *patient files* will be queried for demographic information, combatant or civilian status, admission dates, discharge dates, whether the injury was conflict-related or not, geographical site for injury, cause and mechanism of injury, prehospital data, medical history, vital signs at hospital admission, anatomical data and details regarding extent of abdominal injury, number and type of surgeries, details on surgery, need for ICU care, in hospital complications, re-admission including cause of re-admission, outcome including death and cause of death. Paper based data will be entered into a computer database using Epidata entry software (The Epidata Association, Odense, Denmark).

Patient Files

- Time of admission (specified)
- Age in years (specified)
- Sex (Male/Female/Unknown)
- Ethnicity (Arabic/Kurdish/Other/Unknown)
- Civilian/Combatant (Iraqi/Peshmerga/ISg/Unknown/Other)
- Time of injury (specified)
- Geographical location where injury occurred (specified)
- War-related injury (Yes/No/Unknown)
- Cause of injury (Bullet/Shell/Mie/IED/Unknown/Other)
- Mechanism of injury (Gunshot/Stab/Blast/Crush/Fragment/Burn/Traffic accident/Unknown/Other)
- Care prior to admission to EH (First Aid/Medical/Surgery/None given/Unknown)
- Provider of care prior to EH (MSF/Aspen/ICRC/Samaritan Purse/DoH/None)
- Mode of transport to EH (Military/Private car/Motorcycle/Ambulance/Unknown)
- Medical history (Healthy/Prior surgery/ Prior medical/Unknown)
- Body temperature (specified in Celsius)
- Heart rate (specified in beats/min)
- Blood pressure (specified in systole/diastole mmHg)
- Pregnant (Yes/No/Unknown)
- Pregnancy status based on (Lab/Question/Status/Unknown)
- Site and extent of abdominal wound (specified)
- Other injuries (Yes/No/Unknown, specified)
- Preoperative haemoglobin (specified in g/dL)
- Preoperative transfusions (Yes/No/Unknown, specified)
- Use of preoperative radiology (Yes/No/Unknown, specified)
- Time and date of procedure (specified)
- Duration of procedure (specified in hours and minute)

- Antibiotics prophylaxis (Yes/No/Unknown, specified)
- Procedure done (appendix 1 for definition of findings)

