- Perioperative complication (Yes/No/Unknown, specified)
- Postoperative antibiotic prophylaxis (Yes/No/Unknown, specified)
- Postoperative infection (Yes/No/Unknown, appendix 3 for definition)
- Other postoperative complication (Yes/No/Unknown, appendix 2 for definition)
- Need of postoperative intensive care (Yes/No/Unknown, specified)
- Postoperative transfusions (Yes/No/Unknown, specified)
- Use of postoperative radiology (Yes/No/Unknown, specified)
- Further surgery done (Yes/No/Unknown, specified)
- Discharge (Yes/No/Unknown, specified)
- Follow-up scheduled (Yes/No/Unknown, specified)
- Re-admission (Yes/No/Unknown, specified)
- Deceased during hospital stay (Yes/No/Unknown, specified)
- Remarks

Statistical Analyses

Sample Size

Due to the nature of the study, the sample size will be a convenience sample of the available cases during the study period. It is expected that approximately 160 subjects will be enrolled.

Statistical Methods

Analysis will be done by as treated. A 5% significance level will be used. The difference in dichotomous, such as postoperative complication (primary outcome), and categorical outcomes with more than two categories will be tested using chi-square or Fisher test. For differences in continuous variables t-test will be used. In order to adjust our analysis for possible confounders and effect modifiers we will then use linear, logistic, ordinal or multinomial regression models, according to the nature of the outcome (continuous, binary, ordinal or nominal) with injury mechanism as the dependent variable and civilian/combatant as the main explanatory variable. Important demographic and injury specific parameters such as geographical location, date, age, sex, and injured organs, will then be included in the model as potential confounders.

Safety and Monitoring

Participant Confidentiality

The use of identification numbers will ensure anonymity in the data analysis. The participant's age, gender and demographic characteristics will be used as identifying features for analysis. The research team will ensure the ethical principles of beneficence, non-maleficence, justice and respect of patients are adhered to throughout the study.

Data Collection and Management

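### The adjusted-analysis sentence contradicts itself on the dependent variable, and injured organs, a primary measure that follows civilian/combatant status, is listed as a confounder

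*Combined protocol and SAP*

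**What the plan says.** All of the following is in the Combined protocol and SAP.

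- **Primary outcome and unadjusted tests (Statistical Methods).** Dichotomous outcomes, "such as postoperative complication (primary outcome"), and categorical ones "will be tested using chi-square or Fisher test"; continuous variables get a t-test.
- **Adjusted models (same paragraph).** The regression family is chosen "according to the nature of the outcome (continuous, binary, ordinal or nominal"), yet the models are fitted "with injury mechanism as the dependent variable and civilian/combatant as the main explanatory variable".
- **Covariates (next sentence).** Demographic and injury parameters "such as geographical location, date, age, sex, and injured organs, will then be included in the model as potential confounders".
- **Primary Objective and Primary Measure.** Five things are compared between civilians and combatants: mechanism, organs injured, treatment, complications and outcome.
- **Data, Patient Files.** The mechanism item is unordered: "Mechanism of injury (Gunshot/Stab/Blast/Crush/Fragment/Burn/Traffic accident/Unknown/Other").
- **Justification.** The hypothesis is that indiscriminate weapons in a city injure civilians' abdomens more extensively than combatants'.
- **Appendix 1.** The PATI adds up scores over the injured organs, and complication rates are said to climb steeply once it passes 25.

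The only other text on modelling, the statistical line in the opening summary, names no dependent variable.

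**The concern.** There are two linked defects.

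First, the sentence on adjusted models gives incompatible instructions. Choosing a model family by outcome type implies several dependent variables, but the sentence names one, and it is not the outcome that the paragraph has just called primary.

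Second, injured organs is treated as a confounder. A confounder of the civilian/combatant comparison must not be a consequence of that status. Here the protocol itself presents the organs injured as something to be compared by status, and as a driver of complications.

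At stake is what the adjusted estimate means. On one reading the primary outcome is never adjusted for location, date, age or sex. On the other it is adjusted, but part of the contrast under study is taken out and the result is still labelled a confounder-adjusted difference. Unless the text is corrected, the choice between the readings is made after the data are seen.

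**Working it through.** The plan gives no power, effect size or event rate, so there is no planned figure to reproduce. The check is first textual. The numbers after that only illustrate the mechanism, on assumed inputs.

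**1. The two readings side by side**

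| | Literal reading | One model per outcome |
|---|---|---|
| Dependent variable | Injury mechanism | Each of the five primary measures |
| Use of the four model families | Linear and ordinal models cannot apply to a nominal item | All can apply |
| Primary measures with an adjusted model | 1 of 5; complication not among them | 5 of 5 |
| Place of injured organs | After status, and after the dependent variable (the mechanism produces the organ injury) | After status and before complications; in the organ model, both dependent variable and covariate |

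Neither column makes injured organs a confounder.

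**2. Order of events**

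Status exists before the wound. The hypothesis runs from status to extent of injury, and Appendix 1 runs from injured organs to complications. So on the protocol's own logic the organs lie between status and the primary outcome.

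**3. Hand example (assumed inputs)**

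One organ is injured in 25% of combatants and 45% of civilians. Complication risk is 20% without that injury and 50% with it, and nothing else differs.

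- Combatants: 0.75 × 0.20 + 0.25 × 0.50 = 0.275
- Civilians: 0.55 × 0.20 + 0.45 × 0.50 = 0.335
- Crude OR = (0.335/0.665) / (0.275/0.725) = 1.33
- OR within each organ stratum = 1.00, by construction

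With 35% of civilians injured instead, their risk is 0.65 × 0.20 + 0.35 × 0.50 = 0.305 and the crude OR is 1.16, again going to 1.00.

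**4. Fourteen-organ simulation (assumed inputs except the Appendix 1 risk factors)**

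- Organ frequencies in combatants: duodenum .06, pancreas .05, liver .20, large intestine .35, major vascular .08, spleen .10, kidney .10, biliary .04, small bowel .45, stomach .15, ureter .03, bladder .08, bone .10, minor vascular .15; organs independent.
- Grades 1 to 5 with probabilities .20/.25/.25/.20/.10; 40% civilians; logit(complication) = −1.6 + 0.05 × PATI.
- 300,000 patients; logistic regression on status, without and with 14 organ indicators.

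| How civilians differ | OR without organs | OR with organs |
|---|---|---|
| Organs hit, organ OR 1.4 | 1.21 | 0.99 |
| Organs hit, organ OR 1.8 | 1.44 | 1.00 |
| Organ OR 1.8, plus one grade with probability 0.5 | 1.68 | 1.15 |
| Grade within organ only (one grade up, capped at 5) | 1.27 | 1.30 |

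Simulation error is a few hundredths. In the last row the organs do not differ by group, so adjustment removes nothing.

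**5. Mechanism as dependent variable (assumed inputs, exact probabilities)**

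Half the patients are civilians. Blast or fragment injury occurs in 40% of combatants, with a status–mechanism OR of 2.25, and the logit of multi-organ injury is −0.85 plus the mechanism and status effects. Adding organs to the model changes the status OR as follows:

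- both effects on organs at OR 2: 2.25 to 2.00
- one at 2 and the other at 4: 2.25 to 1.79
- both at 4: 2.25 to 1.48
- only one of the two effects present: stays at 2.25

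**6. Precision**

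The plan states: "It is expected that approximately 160 subjects will be enrolled". With 96 combatants and 64 civilians (40% assumed) and complication rates of .308 and .391, SE(log OR) = √[1/(96 × .308 × .692) + 1/(64 × .391 × .609)] = .338. The 95% CI multiplies and divides the OR by exp(1.96 × .338) = 1.94. The matter is therefore what is estimated, more than how often p falls below 0.05.

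**The case against.** **The mechanism phrase is a drafting slip.** The plan does not say that mechanism is the sole dependent variable, and four model families make sense only with several outcomes. This stands as far as it goes. A reader might infer that the investigators intend to model nothing but mechanism; the text does not support that, only that it contradicts itself. Correcting the slip is not enough, though, because it places injured organs in the complication model.

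**The covariate list is illustrative.** It is introduced by *such as* and speaks of potential confounders. But injured organs is one of only five items named, and nothing tells the analyst to leave it out of any model.

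**Comparing complications among patients with similar organ injuries is a fair case-mix question.** Agreed. The fault is the label, and the absence of an adjusted model without organs beside it.

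**The unadjusted tests remain.** They do. A reader might infer that the civilian/combatant difference would disappear from the report. It would not: the crude difference is still planned, and what is missing is the difference adjusted for confounders but not for its own pathway.

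**The organ-adjusted estimate could be read as a direct effect of status.** That needs an assumption the documents do not give, namely that nothing unmeasured affects both the organs injured and complications. It is safer to call it an organ-adjusted association.

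**Conclusion.** The concern holds and should be fixed. The contradiction over the dependent variable is on the face of the text, and no other section resolves it. That injured organs follows status is an inference, but one drawn from the protocol's own hypothesis, primary measure and Appendix 1. It is not a confounder of the civilian/combatant comparison on either reading.

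The size cannot be derived from the documents. On assumed inputs the effect on a complication OR runs from complete removal (1.33 to 1.00) to practically none (1.27 to 1.30), depending on whether the groups differ in which organs are hit or only in how badly. With mechanism as dependent variable it runs from none to 2.25 falling to 1.48. A reader might infer that the adjusted result is bound to be null; the last row of the fourteen-organ table shows that this does not follow.

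**What to change.** Before analysis, make two changes to Statistical Methods.

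(a) Replace the adjusted-model sentence with wording such as: *For each primary measure in turn (mechanism of injury, organs injured, treatment given, postoperative complication, outcome), a regression model of the matching type is fitted with that measure as dependent variable and civilian/combatant status as the exposure of interest.*

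(b) Take injured organs off the confounder list of these models. If an organ-adjusted model for complications or outcome is wanted, report it separately as an organ-adjusted association, not as the confounder-adjusted difference.

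Change (b) concerns the civilian/combatant models only. Nothing here argues against adjusting for organs in the prior-surgery and 24-hour comparisons, where the organ injury comes before the grouping.

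The cost is a few sentences and a few more models on data already planned for collection, with no extra patients. The downside is imprecision for rare outcomes. At the lowest mortality in Table 1 (7.4%), with 96 and 64 patients, even the unadjusted 95% CI factor is exp(1.96 × √[1/(96 × .074 × .926) + 1/(64 × .074 × .926)]), about 3.3. At the highest (33.3%) the same formula gives about 2.0.

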The battle of Mosul was characterized by the use of improvised explosive devices, human shields and suicide bombers in an urban setting. It is unclear whether this type of warfare cause more extensive abdominal injuries to civilians than combatants. Understanding of the correlation between the severity of abdominal injuries, type of warfare and population affected is of importance when planning for surgical care in a conflict setting.

Aim

To assess whether civilians obtain more extensive abdominal injuries than combatants in an urban battle characterized by the use of indiscriminate weapons.

Study Design

An observational retrospective cohort study with longitudinal data collection.

All patients admitted with penetrating abdominal injury subjected to an exploratory laparotomy at Emergency Hospital, Erbil, between October 17, 2016 and July 16, 2017 will be included. Differences in demographics, injury mechanism, time since injury, clinical status on arrival, intraoperative findings, postoperative complications and outcome will be analysed.

Primary Objective

Differences in injury mechanism, organs injured, surgical treatment given, postoperative complications and outcome between civilians *and* combatants.

Secondary Objectives

Differences in surgical treatment given, postoperative complications and outcome between patients with prior surgical treatment of their injury *and* patients without prior surgical treatment.

Differences in surgical treatment given, postoperative complications and outcome between patients who receive surgical treatment less than 24 hours from injury *and* patients who receive surgical treatment more than 24 hours from injury will be analysed.

Statistical methods

Differences between groups will be analysed using t-test and regression models.

List of Abbreviations

EH	Emergency Hospital, Erbil, Iraq
Ex-lap	Exploratory laparotomy
ICRC	International Committee of the Red Cross
IED	Improvised Explosive Device
ISg	Islamic State Group
WHO	World Health Organization

List of Definitions

Civilians	Children <16 years, all women and men \geq 50 years.
Combatants	Men 16-50 or combatants by own admission.
Exploratory laparotomy	Surgical incision through the abdominal wall into the abdominal cavity
PATI	Penetrating Abdominal Trauma Index Assess the severity of injury in patients with knife, gunshot or other penetrating wounds to the abdomen (appendix 1).

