Appendix 4: Case Report Form

Exploratory laparotomy following penetrating abdominal injuries: a cohort study from a referral hospital in Erbil, Kurdistan region in Iraq

Case Report Form

1 November 2017

FINAL version

Case Report Form (CRF), version 171101, protocol: _____

Patient Data

Patient no

1. Time of admission

 / /

day month year

 :

hours minutes

Unknown

2. Age

 in years

Unknown

3. Sex

Male

Female

Unknown

4. Ethnicity

Arabic

Kurdish

Other

Unknown

If other, specify

5. Civilian/Combatant

Civilian

Combatant

Unknown

If combatant

Iraqi

Peshmerga

IS

Unknown

Other

If other, specify

Investigators signature _____

day month year

Validated by and date: _____

Case Report Form (CRF), version 171101, protocol: _____

Injury Data

Patient no

[figure not shown]
6. Time of injury

hours minutes

day month year

Unknown

7. Geographical location where injury occurred

Unknown

Other

If other, specify location where injury occurred

Investigators signature

day month year

Validated by and date: _____

Case Report Form (CRF), version 171101, protocol: _____

Injury Data continued

Patient no

8. War-related injury

Yes

No

Unknown

9. Cause of injury

(If several causes number in same order as question 20 and 21)

Bullet

Shell

Mine

IED

Unknown

Other

If other, specify

10. Mechanism of injury

(If several number in same order as question 20 and 21)

Gunshot

Stab

Blast

Crush

Fragment

Unknown

Burn

Other

Traffic accident

If other, specify

Investigators signature _____

_____/_____/_____
day month year

Validated by and date: _____

Case Report Form (CRF), version 171101, protocol: _____

Prehospital Care Data

Patient no

11. Care prior to admission to EH

(If several number in chronological order)

First aid

Medical

None given

Unknown

Surgery

If surgery, specify procedure done

day month year

of procedure

12. Provider of care prior to EH

(If several number in chronological order)

MSF

Aspen

ICRC

Unknown

Samaritan Purse

None

Department of Health

Other, specify

Investigators signature

day month year

Validated by and date: _____

Case Report Form (CRF), version 171101, protocol: _____

Prehospital Care Data cont.

Patient no

13. Mode of transport to EH

(If several number in chronological order)

Military

Private car

Motorcycle

Ambulance

Unknown

Other, specify

14. Medical history

Healthy

Unknown

Prior surgery

Prior medical

If prior surgery specify procedure(s)

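### Civilian status is defined almost entirely by age and sex, yet the models adjust for age and sex, so the adjusted effect rests on modelling assumptions and not on comparable patients

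*Combined protocol and SAP*

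**What the plan says.** The List of Definitions in the combined protocol and SAP sets two rules. Civilians are "Children <16 years, all women and men" aged 50 or over. Combatants are "Men 16-50 or combatants by own admission". A man aged exactly 50 meets both.

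For the adjusted analyses, Statistical Methods says "we will then use linear, logistic, ordinal or multinomial regression models", chosen by outcome type, with "civilian/combatant as the main explanatory variable". It names as covariates "Important demographic and injury specific parameters such as geographical location, date, age, sex, and injured organs", and it commits to using them: they "will then be included in the model as potential confounders". It gives no functional form for age, no age-by-sex term and no check of overlap.

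Status is also a recorded item. Under Data Sources, the patient files "will be queried for demographic information, combatant or civilian status". The case report form (Appendix 4) has an item "5. Civilian/Combatant" with an unknown option and an affiliation field for combatants. The documents do not say whether this item follows the List of Definitions rule or was determined independently of it.

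**The concern.** Adjustment for a confounder works by comparing exposed and unexposed patients who are alike on it. Under the written rule no man aged 16–49 can be a civilian, and a woman, a child or an older man can be a combatant only by declaring it. Apart from that route, whose number is not given, the exposure is a deterministic function of two of its own covariates and there are no like-for-like patients to compare.

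An additive regression will still return a coefficient. It would be read as a confounder-controlled effect of being a civilian, which is the study's central question. It would in fact depend on how age is modelled and on age and sex acting additively, which the data can check weakly or not at all. The plan states neither assumption.

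**Working it through.** The plan has no figure to reproduce: the 160 subjects are a convenience sample with no power calculation. The check is therefore structural, followed by illustrations.

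**1. The exposure as a formula.** Leave self-declared combatants aside and use 16–49, because age 50 is ambiguous. Let mid = 1 for ages 16–49 and old = 1 from age 50. Then civilian = 1 − male × mid.

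| | Under 16 | 16–49 | 50 and over |
|---|---|---|---|
| Men | civilian | combatant | civilian |
| Women | civilian | civilian | civilian |

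No cell contains both groups.

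**2. Estimability.** Intercept, civilian, male, mid and old are 5 columns of rank 5, so the additive model can be fitted. Adding male × mid and male × old gives 7 columns of rank 6, because civilian = intercept − male × mid. The civilian coefficient is then not estimable.

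With L the log odds, the additive banded model targets −{[L(men 16–49) − L(women 16–49)] − [L(men, other ages) − L(women, other ages)]}. That is an age-by-sex interaction. It equals a civilian effect only if the sex difference would otherwise be the same at all ages.

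**3. Loss of precision.** The variance inflation factor is VIF = 1/(1 − R²), with R² from regressing civilian on the other terms. The documents give no age-sex mix, so a base mix was assumed: men 16–49 60%, women 15%, children 17%, men from 50 8%. VIF is 1.72 with linear age plus sex, 3.95 with quadratic age and 6.13 with bands. Standard errors therefore grow by √1.72 = 1.31, √3.95 = 1.99 and √6.13 = 2.48.

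**4. Simulations at n = 160.** Assumptions: binary outcome, logistic model, two-sided 5% Wald test, 2,000 runs per scenario. Ranges cover the base mix and mixes with 80% and 45% men 16–49 (women/children/older men 8/8/4 and 22/23/10). Ages are uniform within groups. A dash means not reported.

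| Assumed truth | Unadjusted | Linear age + sex | Quadratic age + sex | Age bands + sex |
|---|---|---|---|---|
| No effect; logit = −1.2 + 0.001(age − 30)² | 18–24% | 18–32% | 4–5% | – |
| Same, curvature halved | 7.5–9.9% | 7–12% | – | – |
| Same, curvature quartered | – | 4–7% | – | – |
| No effect; logit = −1.2 + 0.03 × years over 30 | 7–9% | 7–9% | – | – |
| No effect; age truly linear, 0.02 per year | – | 3–5% | – | – |
| No effect; women 16–49 at +0.7 log odds (base mix) | 9%, OR 1.2 | 5%, OR 1.0 | 8%, OR 1.4 | 13%, OR 2.1 |
| True civilian OR 2.5, no age effect (power) | 62–80% | 35–59% | 17–32% | 9–25% |

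Percentages are rejection rates; OR is the median civilian odds ratio. The banded result in the sixth row follows from step 2: −{(0 − 0.7) − 0} = 0.7, and exp(0.7) = 2.01, against 2.08 simulated.

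**5. A second set of assumptions.** This used 400,000 simulated patients; 70, 80 or 90% male; 25% under 16, 63% aged 16–49, 12% older; and no civilian effect.
- If the young and old have twice the odds of those aged 16–49, the civilian OR is 1.99–2.01 with linear age, 1.47–1.74 with quadratic age and 0.99–1.02 with bands.
- If adult men have half the odds for reasons unrelated to status, every additive model gives 1.90–2.05.

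**6. Self-declared combatants.** If 2, 5 or 10 of 160 were self-declared combatants among rule-defined civilians aged 14 or over, the model with band-by-sex terms becomes estimable, with VIF 19.9, 8.4 and 4.6. The estimate then hangs on those few patients.

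**The case against.** The strongest reply is that the defect exists only if the age-sex rule generates the exposure. Status is queried separately from demographics, and the form has its own item with an unknown option, which is compatible with independent classification. Men 16–49 could then be recorded as civilians and there would be overlap. This stands as a condition. But the List of Definitions is the only written rule, and nothing says the form overrides it.

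Second, removing age and sex is not better on error rates. Under the strong U-shape the unadjusted comparison rejects in 18–24% of runs, against 4–5% with quadratic age; when additivity fails it rejects in 9%, against 5% with linear age. That is true if the result is still called a civilian effect. Once it is described as women, children and older men versus men 16–49, those rejections reflect a real difference between those groups. The gain is an honest label, not less confounding. Keeping age and sex with a stated age form, sensitivity models and limited interpretation is arguable, but that result could not be presented as confounder-controlled.

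Third, the large false-positive rates need a steep curve: risk of about 23% at age 30 and 60% at age 70. Weaker curves give rates near nominal, and the 13% for banded age is for the base mix only (about 6% with 80% men 16–49). These figures show what is possible, not the expected bias.

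Fourth, the plan does not call for band-by-sex terms, and it names injury mechanism, a multi-category variable, as the dependent variable, whereas the simulations use a binary outcome. The percentages do not carry over to that model. The lack of overlap does, because it lies in the covariates.

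**Conclusion.** The concern holds and should be fixed before analysis. If status follows the written rule, the non-estimability with age-band-by-sex terms is exact and needs no assumed data. Under the additive adjustment that the plan implies, one null truth can give a civilian odds ratio of about 2.0 or 1.0 depending only on how age is entered, and a sex difference confined to adults cannot be told apart from a civilian effect. More flexible age terms reduce bias from a wrong age shape but cost most of the power (base mix, true OR 2.5: 80% unadjusted, 27% quadratic, 21% banded).

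These magnitudes rest on assumed mixes and risk curves. The conclusion assumes few or no self-declared combatants outside men 16–49, and that the form item does not replace the definition. The defect concerns the adjusted models: the chi-square or Fisher test named for the primary outcome has no age or sex term, although it too compares men 16–49 with everyone else.

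**What to change.** First, state which status variable is the exposure, and reconcile the two definitions for a man aged exactly 50. Then:

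- **If the age-sex rule is the exposure:** remove age and sex from the adjusted models, describe the contrast as women, children and older men versus men aged 16–49, and do not present it as a confounder-controlled effect of civilian status. This relabels the contrast; it does not remove confounding by age.
- **If the recorded status (form item 5) was determined independently of age and sex:** use it as the exposure, tabulate it by sex and age band first, and adjust for sex and flexibly for age. Add a comparison restricted to men 16–49 only if some of them are recorded as civilians.

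The cost is SAP wording, one cross-tabulation and a re-specified model, with no new data. The downside is that the restricted comparison has fewer patients and may be empty, while the rule-based result supports a narrower conclusion and stays confounded by age.
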